5.0 Stratification Factors OR Grouping Factor: N/A

6.0 Registration/Randomization Procedures

- 6.1 Pre-Registration (Step 0)
 - 6.11 To pre-register a patient, access the ACCRU web page at **Second Second** go to the Application section and click on "Registration" and enter the registration/randomization application. The registration/randomization application is available 24 hours a day, 7 days a week. Back up and/or system support contact information is available on the Web site. If unable to access the Web site, call the Academic and Community Cancer Research United (ACCRU) Registration Office at **Sector** between the hours of 8 a.m. and 4:30 p.m. Central Time (Monday through Friday).

Users should refer to the section titled "Pre-Registration Components" for details on how to pre-register a patient to a study. At the time of pre-registration the patient will receive an ACCRU patient identification number. This number is to be used when submitting paper confirmation of the presence of a BRAF^{V600E} mutation for the study. Patient pre-registration via the registration/randomization application can be confirmed in any of the following ways:

- Contact the ACCRU Registration Office I If the patient was pre-registered, the ACCRU Registration Office staff can access the information from the centralized database and confirm the registration.
- Refer to "Application Training" at **Example 19**; click on "Registration, Installation & Entry Instructions".
- 6.12 Documentation of IRB approval must be on file in the Registration Office before an investigator may register any patients. Approvals should be uploaded using the online ACCRU Regulatory Management System (ARMS).

In addition to submitting initial IRB approval documents, ongoing IRB approval documentation must be on file (no less than annually) with ACCRU. Approvals should be uploaded using the online ACCRU Regulatory Management System (ARMS). If the necessary documentation is not submitted in advance of attempting patient registration, the randomization will not be accepted and the patient may not be enrolled in the protocol until the situation is resolved.

Submission of annual IRB approvals is required until the study has been closed through your IRB.

- 6.13 Prior to accepting the pre-registration, the registration/randomization application will verify the following:
 - IRB approval at the registering institution
 - Patient pre-registration eligibility
 - Existence of a signed consent form

- Existence of a signed authorization for use and disclosure of protected health information
- 6.14 Pre-registration tests/procedures (see Section 4.0) must be completed within the guidelines specified on the test schedule.
- 6.15 Submission of central electronic/paper confirmation of the presence of a BRAF^{V600E} mutation.
 - 6.151 Once the patient has completed the pre-registration step, sites will complete the top portion of the central review form and email it to along results from a CLIA/CAP certified testing lab (commercial or institutional) that confirm the presence of a BRAF^{V600E} mutation in the patient's tumor for central review.
- 6.2 Registration (Step 1)

Upon completion of the patient's central review, the person provided on the central review form will be contacted by email with the results approximately one week after submission. If based upon the review the subject is approved for registration, the site will send the central review form to the ACCRU Registration Office via fax for the pre-registering institution must register the subject to the protocol.

6.21 To register a patient, access the ACCRU web page at Application, go to the Application section and click on "Registration" and enter the registration/randomization application. The registration/randomization application is available 24 hours a day, 7 days a week. Back up and/or system support contact information is available on the Web site. If unable to access the Web site, call the Academic and Community Cancer Research United (ACCRU) Registration Office at between the hours of 8 a.m. and 4:30 p.m. Central Time (Monday through Friday).

Users should refer to the section titled "Pre-Registration Component" for details on how to register a patient on step 2 of a study that has a pre-registration and registration step. The instructions for the registration/randomization application are available using the Help button. Prior to initiation of protocol treatment, this process must be completed in its entirety and an ACCRU subject ID number must be available as noted in the instructions. It is the responsibility of the individual registering the patient to confirm the process has been successfully completed prior to release of the study agent. Patient registration via the registration/randomization application can be confirmed in any of the following ways:

- Contact the ACCRU Registration Office **Contact** If the patient was pre-registered, the ACCRU Registration Office staff can access the information from the centralized database and confirm the registration.
- Refer to "Application Training" at click on "Registration, Installation & Entry Instructions".
- 6.22 Correlative Research

A mandatory correlative research component is part of this study, the patient will be automatically registered onto this component (see Sections 3.0, 14.0 and 17.0).

- 6.23 Prior to accepting the registration, the registration/randomization application will verify the following:
 - Patient eligibility
- 6.24 At the time of registration, the following will be recorded:
 - Patient has/has not given permission to store and use his/her blood sample(s) for future research to learn about, prevent, or treat cancer.
 - Patient has/has not given permission to store and use his/her blood sample(s) for future research to learn, prevent, or treat other health problems (for example: diabetes, Alzheimer's disease, or heart disease).
 - Patient has/has not given permission to store and use his/her tissue sample(s) for future research to learn about, prevent, or treat cancer.
 - Patient has/has not given permission to store and use his/her tissue sample(s) for future research to learn, prevent, or treat other health problems (for example: diabetes, Alzheimer's disease, or heart disease).
 - Patient has/has not given permission for ACCRU to give his/her sample(s) to outside researchers.
- 6.25 Treatment on this protocol must commence at an ACCRU institution under the supervision of a medical oncologist.
- 6.26 Treatment cannot begin prior to registration and must begin ≤14 days after registration.
- 6.27 Pretreatment tests/procedures (see Section 4.0) must be completed within the guidelines specified on the test schedule.
- 6.28 All required baseline symptoms (see Section 10.3) must be documented and graded.
- 6.29a Blood draw kit is available on site.

7.0 Protocol Treatment

- 7.1 Treatment Schedule Starting Day 1 of Cycle 1 (28 day Cycles), patient will self-administer:
 - Encorafenib 450 mg orally daily
 - Binimetinib 45 mg orally twice daily
- 7.2 Anti-cancer treatment by a local medical doctor (LMD) is not allowed. However, symptom management that cannot wait until the next visit to the study site can be handled by the LMD.

8.0 Dosage Modification Based on Adverse Events

Strictly follow the modifications in this table for the first **two** cycles, until individual treatment tolerance can be ascertained. Thereafter, these modifications should be regarded as guidelines to produce mild-to-moderate, but not debilitating, side effects. If multiple adverse events are seen, administer dose based on greatest reduction required for any single adverse event observed. Reductions or increases apply to treatment given in the preceding cycle and are based on adverse events observed since the prior dose.

ALERT: ADR reporting may be required for some adverse events (See Section 10)

8.1 Dose Levels (Based on Adverse Events in Tables 8.2 and 8.3), if applicable – This is potentially different information than what is found in the tables in Section 7.0.

Dose		
Level	Encorafenib	Binimetinib
0	450 mg	45 mg
-1	300 mg	30 mg
-2	225 mg	15 mg

* Dose level 0 refers to the starting dose.

The lowest recommended dose level of encorafenib is 225 mg QD and the lowest recommended dose level of binimetinib is 15 mg BID. When the AE that resulted in a dose reduction improves to and remains stable at the patient's baseline level for a minimum of 14 days, the dose can be re-escalated to the next dose level at the discretion of the Investigator, provided there are no other concomitant toxicities that would prevent drug re-escalation. There is no limit to the number of times the patient can have their dose reduced or re-escalated, however:

- No dose re-escalation of encorafenib is allowed after a dose reduction due to prolonged QTcF ≥ 501 msec
- No dose re-escalation of binimetinib is allowed after a dose reduction due to LVEF dysfunction
- No dose re-escalation of binimetinib or encorafenib is allowed after a dose reduction due to retinal toxicity ≥ Grade 2.
- If binimetinib is withheld, consider reducing encorafenib to a maximum dose of 300 mg daily until binimetinib is resumed.

Please refer to Dose Modification Table for recommended dose modifications for encorafenib and/or binimetinib, if applicable, based on the occurrence of treatment-related AEs.

8.2 Recommended Encorafenib Dose Modifications

→ → Use the NCI Common Terminology Criteria for Adverse Events (CTCAE) version 5.0* unless otherwise specified \leftarrow ←

CTCAE				
System/Organ/Class	ADVERSE EVENT			
(SOC)		ACTION**		
BASED ON INTERVAL ADVERSE EVENT				
	Non-cutaneous RAS	Permanently discontinue		
	mutation-positive			
	malignancies			
Eye Disorder	Uveitis			
	Grade 1-3	If Grade 1 or 2 does not respond to specific ocular		
		and himimatinih for un to 6 wools		
	Crede 4	Demonstrative discontinue encourter it and triving time		
	Grade 4	Permanently discontinue encoratenit and binimetinit		
	specify			
	Grade 1-2	Maintain dose level of encorafenib and binimetinib and increase frequency of ophthalmic monitoring to at least every 14 days until stabilization or resolution.		
	Grade 3	 Interrupt dosing of encorafenib and binimetinib and refer patient to ophthalmologist within 7 days. If resolved to Grade ≤ 1 in ≤ 21 days, resume treatment at 1 reduced dose level of encorafenib and binimetinib. If not resolved to Grade ≤ 1 in ≤ 21 days, permanently discontinue encorafenib and binimetinib and close follow-up with ophthalmic monitoring until stabilization or resolution. 		
	Grade 4	Permanently discontinue encorafenib and binimetinib and immediate follow-up with ophthalmic monitoring until stabilization or resolution.		
Investigations	Electrocardiogram QT corrected interval prolonged			
	QTcF > 500 ms and ≤ 60 ms increase from baseline	 1st occurrence: Temporarily interrupt dosing of encorafenib until QTcF < 500 ms. Then resume treatment at 1 reduced dose level of encorafenib. 2nd occurrence: Temporarily interrupt dosing of encorafenib treatment until QTcF < 500 ms. Then resume treatment at 1 reduced dose level of encorafenib. 3rd occurrence: Permanently discontinue encorafenib. 		

\rightarrow \rightarrow Use the NCI Common Terminology Criteria for Adverse Events (CTCAE) version 5.0* unless otherwise specified \leftarrow			
CTCAE System/Organ/Class (SOC)	ADVERSE EVENT	ACTION**	
	QTcF > 500 ms and > 60 ms increase from baseline	Permanently discontinue encorafenib.	
	Alanine aminotransferase or aspartate aminotransferase increased		
	Grade 2	 Maintain encorafenib dose. If no improvement within 4 weeks, withhold encorafenib until improved to Grade 0-1 or to pretreatment/baseline levels and then resume at the same dose. 	
	Grade 3 or 4	See Other Adverse Reactions	
	Investigations-Other, specify		
	Recurrent Grade 2 or First occurrence of any Grade 3	 Withhold for up to 4 weeks. If improves to Grade 0-1 or to pretreatment/baseline levels, resume at reduced dose. If no improvement, permanently discontinue encorafenib. 	
	First occurrence of ay Grade 4	 Withhold for up to 4 weeks. If improves to Grade 0-1 or to pretreatment/baseline levels, then resume at a reduced dose. If no improvement, permanently discontinue encorafenib. 	
	Recurrent Grade 3	Consider permanently discontinuing encorafenib and binimetinib.	
	Recurrent Grade 4	Permanently discontinue encorafenib and binimetinib.	
Skin and subcutaneous tissue disorders	Palmar-plantar erythrodysesthesia syndrome		
	Grade 1	Maintain dose of encorafenib. Promptly institute supportive measures, such as topical therapy, for symptomatic relief. Give instruction on life-style modifications.	

→ → Use the NCI Common Terminology Criteria for Adverse Events (CTCAE) version 5.0* unless otherwise specified $\leftarrow \leftarrow$		
CTCAE System/Organ/Class (SOC)	ADVERSE EVENT	ACTION**
	Grade 2	1 st occurrence:
		• Maintain dose of encorafenib and HFSR should be closely monitored. Promptly institute supportive measures, such as topical therapy, for symptomatic relief. Give instruction on life-style modifications.
		 If no improvement ≤ 14 days, interrupt dosing of encorafenib until resolved to Grade ≤ 1. Resume treatment with encorafenib at current dose level. Continue supportive measures, such as topical therapy, for symptomatic relief. Give instruction on life-style modifications.
		Additional occurrence:
		• Treatment with encorafenib may be maintained or interrupted based upon the Investigator's discretion. Continue supportive measures, such as topical therapy, for symptomatic relief. Give instruction on life-style modifications.
		If interrupted dosing of encorafenib per Investigator's judgment, interrupt until resolved to Grade ≤ 1 . Resume treatment with encorafenib at the same dose level or 1 reduced dose level based upon the Investigator's discretion.

\rightarrow \rightarrow Use the NCI Common Terminology Criteria for Adverse Events (CTCAE) version 5.0* unless otherwise specified $\leftarrow \leftarrow$			
CTCAE System/Organ/Class (SOC)	ADVERSE EVENT	ACTION**	
	Grade 3	1 st or additional occurrence:	
		Interrupt dosing of encorafenib until resolved to Grade ≤ 1. Promptly initiate supportive measures, such as topical therapy, for symptomatic relief. Give instruction on life- style modifications. Reassess the patient weekly. Then resume treatment at one reduced dose level of encorafenib.	
		• Consider referral to dermatologist and manage HFSR per dermatologist's recommendation.	
		$> 3^{nd}$ occurrence: Interrupt dosing of encorafenib until resolved to Grade ≤ 1 , decision to resume treatment with encorafenib at one reduced dose level or permanently discontinue encorafenib should be based upon the Investigator's discretion.	
	Skin and subcutaneous tissue disorders-Other, specify		
	Grade 2	If no improvement within 2 weeks, withhold until Grade 0-1. Resume at same dose if first occurrence or reduce dose if recurrent.	
	Grade 3	Withhold until Grade 0-1. Resume at same dose if first occurrence or reduce dose if recurrent.	
	Grade 4	Permanently discontinue encorafenib.	
Gastrointestinal	Nausea/Vomiting		
disorders	Grade 1-2	Maintain dose level of encorafenib and binimetinib. Promptly institute antiemetic measure.	
	Grade 3	Interrupt dosing of encorafenib and binimetinib until resolved to Grade ≤ 1 . Then resume treatment at 1 reduced dose level of encorafenib. Resume treatment with binimetinib at the current dose if, in the judgment of the Investigator, the toxicity is considered to be unrelated to binimetinib, or at 1 reduced dose level. Note: Interrupt dosing of encorafenib and binimetinib	
		for \geq Grade 3 vomiting or Grade 3 nausea only if the vomiting or nausea cannot be controlled with optimal antiemetics (as per local practice).	
	Grade 4	Permanently discontinue encorafenib and binimetinib.	

- ****** Use the following to describe actions in the Action column:
 - Modified=A modification indicates a change in dose level during the current cycle. However, if a modification was issued after the last dose was received in the current cycle, the modification should be reported on the subsequent cycle. "Yes, planned" should be selected if the dose level was changed according to protocol guidelines (i.e. due to adverse events, lab values, etc.); "Yes, unplanned" should be selected if the dose level change was not a part of protocol guidelines (e.g. vacation, mistake, etc.). Held doses (including omissions and delays) should not be reported as modifications.
 - Omitted=An omission indicates a dose was skipped and not made up, or that the drug was discontinued.
 - Delayed=A delay indicates dose was postponed or not received when expected.

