Respiratory, thoracic and mediastinal	Pneumonitis, pulmonary fibrosis		
disorders	Grade 2	 Withhold binimetinib for up to 4 weeks. If improves to Grade 0-1, resume at a reduced dose. If not resolved within 4 weeks, permanently discontinue. 	
	Grade 3 or Grade 4	Permanently discontinue binimetinib.	
Investigations	Alanine aminotransferase or aspartate aminotransferase increased		

$\rightarrow \rightarrow$ Use the NCI C	Common Terminology Crit otherwise	eria for Adverse Events (CTCAE) version 5.0* unless e specified 🗲 🗲
CTCAE System/Organ/Class (SOC)	ADVERSE EVENT	ACTION**
	Grade 2	Maintain binimetinib dose.
		• If no improvement within 2 weeks, withhold binimetinib until improved to Grade 0-1 or to pretreatment/baseline levels and then resume at the same dose.
	Grade 3 or 4	See Other Adverse Reactions
	CPK increased	
Investigations	Grade 4 asymptomatic or Any Grade with symptoms or with renal impairment	 Withhold binimetinib dose for up to 4 weeks. If improved to Grade 0-1 resume at a reduced dose. If not resolved within 4 weeks, permanently discontinue binimetinib.
	Investigations-Other, specify	
	Recurrent Grade 2 or	Withhold for up to 4 weeks.
	First occurrence of any Grade 3	 If improves to Grade 0-1 or to pretreatment/baseline levels, resume at reduced dose. If no improvement, permanently discontinue encorafenib and binimetinib.
	First occurrence of any	Permanently discontinue or withhold for up to 4 weeks.
	Grade 4	 If improves to Grade 0-1 or to pretreatment/baseline levels, then resume at a reduced dose. If no improvement, permanently discontinue encorafenib and binimetinib.
	Recurrent Grade 3	Consider permanently discontinuing encorafenib and binimetinib.
	Recurrent Grade 4	Permanently discontinue.
Gastrointestinal	Nausea/Vomiting	
disorders	Grade 1-2	Maintain dose level of encorafenib and binimetinib. Promptly institute antiemetic measure.

\rightarrow \rightarrow Use the NCI Common Terminology Criteria for Adverse Events (CTCAE) version 5.0* unless otherwise specified \leftarrow		
CTCAE System/Organ/Class (SOC)	ADVERSE EVENT	ACTION**
	Grade 3	Interrupt dosing of encorafenib and binimetinib until resolved to Grade ≤ 1 . Then resume treatment as 1 reduced dose level of encorafenib. Resume treatment with binimetinib at the current dose if, in the judgement of the Investigator, the toxicity is considered to be unrelated to binimetinib, or at 1 reduced dose level.

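### The Grade 3-4 ALT/AST action in both dose tables points to a heading that does not exist, and the likely target row stops one drug in 8.2 but both in 8.3

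*Combined protocol and SAP*

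**What the plan says.** Every patient takes encorafenib and binimetinib (section 7.1). Dose changes are set out in two tables, 8.2 for encorafenib and 8.3 for binimetinib. Section 8.0 introduces them with "Strictly follow the modifications in this table for the first" two cycles; after that they are guidelines.

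In both tables ALT/AST increase is listed under Investigations. Grade 2 has a full instruction. In 8.2 the dose is maintained at first and then, if there is no improvement within 4 weeks, the site is to "withhold encorafenib until improved to Grade 0-1 or to pretreatment/baseline levels and then resume at the same dose". For Grade 3 or 4 the whole entry, in 8.2 and again in 8.3, is "See Other Adverse Reactions".

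Both tables also have an Investigations-Other row with its own Grade 3 and Grade 4 actions. When a first Grade 3 or first Grade 4 event does not improve, 8.2 says "If no improvement, permanently discontinue encorafenib" and the entry ends there; 8.3 says "If no improvement, permanently discontinue encorafenib and binimetinib".

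**The concern.** For the most severe liver-enzyme grades, the instruction that sites must follow strictly refers to something that is not there. A site has to work out which row is meant. Having done so, it finds that the row differs between the tables in what is stopped when the enzymes do not recover.

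The situation is foreseeable. Section 15.17 lists increased AST as very common (at least 10%) with binimetinib. Section 15.27 lists AST and ALT increases as common (1% to under 10%) with encorafenib. Section 3.24 admits patients with liver metastases at up to 5 x ULN. These are not Grade 3-4 rates, and the documents give none, so no patient count can be put on the problem.

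What is at stake is consistent handling of a liver safety event across sites. The response-rate analysis is not involved.

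**Working it through.** No sample size, error rate or event count enters here, so the check is a comparison of text.

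**Step 1: does the target exist?** The phrase used as the pointer occurs only in the two ALT/AST entries. The catch-all rows are named by organ class: Eye disorders-Other, Investigations-Other, and Skin and subcutaneous tissue disorders-Other. None has the pointer's name, and neither does any section. Damage in the public copy is an unlikely explanation: it affects the eye rows of 8.2, while the ALT/AST and Investigations-Other rows are intact in both tables. The pointer therefore fails in 2 of 2 tables.

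**Step 2: which row is meant?** Three features point to Investigations-Other. It is in the same organ class as ALT/AST. It has Grade 3 and Grade 4 actions. In 8.2 its recovery criterion, "If improves to Grade 0-1 or to pretreatment/baseline levels, resume at reduced dose", matches the criterion in the ALT/AST Grade 2 entry quoted above. In 8.2 it directly follows the pointer; in 8.3 the CPK entry lies between. This remains an inference. Read literally, an Other row does not cover an event that has its own named row, so only a working pointer brings ALT/AST into it.

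**Step 3: compare that row across the tables.**

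| Event | 8.2 (encorafenib) | 8.3 (binimetinib) | Agreement |
|---|---|---|---|
| First Grade 3, initial action | Hold up to 4 weeks | Hold up to 4 weeks | Same |
| First Grade 3, no improvement | "If no improvement, permanently discontinue encorafenib" | "If no improvement, permanently discontinue encorafenib and binimetinib" | One drug against two |
| First Grade 4, initial action | Hold up to 4 weeks | "Permanently discontinue or withhold for up to 4 weeks" | 8.3 adds an immediate stop and names no drug |
| First Grade 4, no improvement | As first Grade 3 | As first Grade 3 | One drug against two |
| Recurrent Grade 3 | Consider stopping both | Consider stopping both | Same |
| Recurrent Grade 4 | "Permanently discontinue encorafenib and binimetinib" | Permanent stop, no drug named | Wording only |

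The pointer covers Grades 3 and 4, so it can lead to 4 situations. In 2 (first Grade 3 and first Grade 4) the no-improvement stop differs; 1 (recurrent Grade 4) differs in wording only; 1 (recurrent Grade 3) is identical. 2 + 1 + 1 = 4.

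**Step 4: apply both tables together.** At a first Grade 3, each table holds its own drug. At a first Grade 4, 8.2 holds encorafenib and 8.3 holds or stops. If there is no improvement, 8.3 stops both drugs. The outcome is safe and unambiguous once the row has been found.

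**Step 5: apply 8.2 alone.** Encorafenib is stopped and nothing is said about binimetinib. A reader has some reason to take the one-drug wording as meant. The same row of 8.2 names both drugs for recurrent Grade 4, and genuine one-drug stops exist elsewhere: encorafenib for QTcF above 500 ms with more than 60 ms increase (8.2), and binimetinib for retinal vein occlusion (8.3). The greatest-reduction rule in 8.0 does not settle it, because it concerns several adverse events in one patient, not one event listed in two tables. Section 8.1 says what to consider for encorafenib while binimetinib is withheld, but has no converse rule.

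**The case against.** The strongest reply is that this is a mislabelled cross-reference with little practical effect. Each table is titled for its own drug, every patient takes both drugs, and section 8.1 ties the dose levels to both tables. A site that consults 8.2 only has no binimetinib rule for the event and is already outside the protocol. The likely row is close at hand, and its first action protects the patient in either table. Different initial options for two different drugs are not in themselves a contradiction, and an unnamed drug in the binimetinib table is most naturally binimetinib.

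Most of this stands, and it limits the point. It rules out two stronger readings that a reader might infer.

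- A reader might infer that the protocol leaves binimetinib running while liver enzymes stay high. It does not: under 8.3 binimetinib is held or stopped from the first day of a first Grade 3 or 4 event, and both drugs stop if there is no improvement. 8.2 is silent on binimetinib; it does not say to continue it.
- A reader might infer that encorafenib has no stated action at a first Grade 4. It has one: the Investigations-Other row of 8.2 says to withhold for up to 4 weeks.

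The reply does not repair the pointer. A strict instruction should not depend on the site inferring its target, least of all for the highest grades. Nor does it explain why the two tables, once the row is found, print different stop rules for the same event.

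**Conclusion.** The point holds as a minor safety-wording correction. The pointer is wrong in both tables. In two of the four situations it can lead to, the stop for non-improvement names one drug in 8.2 and two in 8.3. The risk is limited to sites that cannot identify the target or that treat 8.2 as complete on its own.

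The missing heading is a matter of fact. The comparison of rows rests on one assumption, that Investigations-Other is the intended target, which the protocol does not state.

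Two further extensions are tempting and not supported. A reader might treat this as a flaw in the trial design, but the endpoint, alpha and power are untouched. A reader might also fold in Skin-Other Grade 4, where 8.2 stops one drug and 8.3 stops both. That row is not reached by the ALT/AST pointer, and the deliberate one-drug stops elsewhere mean that a one-drug entry is not by itself an error.

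**What to change.** 1. In both 8.2 and 8.3, redirect the Grade 3 or 4 ALT/AST entry to Investigations-Other, specify, or print the Grade 3 and Grade 4 actions in the ALT/AST row itself.
2. Use the same drug-named wording for the no-improvement stop in both tables. Both drugs, as 8.3 already says, is the natural choice; the sponsor's clinical team should confirm it.
3. Name the drug or drugs in the first Grade 4 and recurrent Grade 4 entries of Investigations-Other in 8.3.

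The cost is a wording amendment to two tables and a notice to sites. It adds no visits, tests or patients, and the two-drug stop is already required by 8.3.
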